2.2. Study Objectives and Endpoints

Objectives	End	lpoints
Primary	Primary	
To assess the safety and tolerability of single IV doses of GSK2831781 in healthy		Laboratory safety data (haematology, clinical chemistry, urinalysis)
volunteers and psoriasis patients.	•	Vital signs (blood pressure, heart rate, body temperature)
	•	12-lead ECGs
	•	Adverse events
	•	Inflammatory cytokine levels
Secondary Objectives		ondary Endpoints
To evaluate the pharmacology and clinical effect of a single IV dose of GSK2831781 in a DTH model in healthy volunteers.	•	Change from baseline (PPD 1st challenge) of induration diameter from re-challenge at 3 days post-dose Duration of induration in the re-challenge Change from baseline (PPD 1st challenge) of LAG-3+ cells in biopsies of re-challenged skin at 3 days post-dose, measured by IHC
To evaluate the pharmacology of a single IV dose of GSK2831781 in psoriasis patients.		Change from baseline in LAG-3+ cells in lesional biopsies at Day 29 measured by IHC
To evaluate the pharmacokinetics of single IV doses of GSK2831781 in healthy volunteers and psoriasis patients.		GSK2831781 PK parameters following single intravenous dose: AUC(0-∞), AUC(0-t), AUC(0-Week4), %AUCex, Cmax, tmax, tlast, CL, Vss, MRT, λz and t ½ when assessable
To evaluate the immunogenicity of GSK2831781 administered as a single IV dose in healthy volunteers and psoriasis patients.	•	Antibodies to GSK2831781 in serum
To evaluate the effect of a single IV dose of GSK2831781 on disease activity in psoriasis patients.	•	Change from baseline and actual PASI scores at Day 15, 29, 43, 85, 121 and follow-up
	•	Proportion of subjects who achieve ≥50% and ≥75% improvement from baseline in PASI score at Day 15, 29, 43, 85, 121 and follow-up (PASI 50 and PASI 75)
		Change from baseline and actual PLSS scores at Day 15, 29, 43, 85, 121 and follow-up
		Change from baseline and actual PGA scores at Day 15, 29, 43, 85 and 121
	•	Proportion of subjects in each PGA score category at Day 15, 29, 43, 85 and 121
	•	Proportion of subjects achieving PGA 0/1 and at least a 2-point improvement at Day 15, 29, 43, 85 and 121

Objectives	Endpoints		
Exploratory Objectives	Exploratory Endpoints		
To evaluate the effect of a single IV dose of GSK2831781 in psoriasis patients on biomarkers.	 Histopathological scoring of psoriatic lesional biopsies in subjects with psoriasis - Ki67, CD3 and epidermal thickness 		
	 Transcriptomic analysis of psoriatic lesional biopsies in subjects with psoriasis 		
To evaluate the effect of a single IV dose of GSK2831781 in healthy volunteers and psoriasis patients on pharmacodynamic biomarkers.	Proof of pharmacology biomarker endpoints may include, but not limited to, the following as data permit: • LAG-3 expression on different blood immune cell populations including T-cells • Transcriptomic profiling to assess mRNA levels in peripheral blood • Quantification of LAG-3 mRNA in whole blood • Inflammatory cytokine levels • sLAG-3 concentrations • NK cell CD16 receptor occupancy in whole blood • NK cell activation marker expression in whole blood		
To explore the impact of pre-existing ADAs on the PK of GSK2831781	 GSK2831781 PK parameters following single intravenous dose: AUC(0-∞), AUC(0-t), AUC(0-Week4), %AUCex, Cmax, tmax, tlast, CL, Vss, MRT, λz and t ½ when assessable 		

	Subjects in Cohort 8 (1.5mg/kg) and Cohort 9 (5mg/kg) who have not yet had a follow up visit when protocol amendment 10 is approved should have final assement, a combined follow up/surveillance visit at day 183 ± 7, or as soon as practically possible if they have already been monitored for longer than 183 ± 7 days after dosing. Subjects in Cohort 8 (1.5mg/kg) who have already completed their follow up visit should have their final assessment, a surveillance telephone call as soon as the protocol amendment is approved.			

2.4. Statistical Analyses

The primary objective is to determine the safety and tolerability of single IV doses of GSK2831781 in healthy volunteers and with mild to moderate psoriasis patients. There are no formal hypotheses being tested in the study; instead an estimation and inference approach will be adopted to evaluate the objectives.

3. PLANNED ANALYSES

3.1. Interim Analyses

Interim Analysis	Details (Protocol Defined)			
Dose escalation	For Parts A and B of the study, review of safety, tolerability, available pharmacokinetic, DTH induration, available biomarker and PD for healthy volunteers or PASI and PLSS for psoriasis patients at the end of each cohort will be performed by DEC to aid decisions to proceed to higher dose strengths or to subjects with pre-existing ADA. This analysis can include review of individual subject data, summaries, graphical presentations and/or statistical analysis.			
	Safety/tolerability data monitoring and the decision to proceed to the next dose level of GSK2831781 or to subjects with pre-existing ADA will be made by the DEC.			
	The GSK Clinical Pharmacology Modeling and Simulation (CPMS) representative will extract PK data (including treatment information) from SMS2000 using unscrambled subject IDs. PK data will provide supporting evidence for each dose modification decision. Importantly, if the emerging PK data is significantly different from the predicted values, adjustment may have to be made to the planned doses. Dose modification decisions will take into account the emerging PK data, new PK prediction for the next dose and thus the expected safety cover for the next dose.			
Interim 1	Formal unblinded interim analysis when the last subject in DTH cohort (cohort 5) has completed W4 visit. Data for healthy volunteers in cohorts 1-5 will be included.			
	The purpose of this interim analysis is to provide the project team and GSK stakeholders with key data to inform internal decision making, in order to plan future studies within the clinical development for the asset.			
	There are no planned implications for the conduct of the study.			
	Appropriate data summaries will be at the subject and treatment group level for key endpoints of interest and the circulation of results will be restricted to selected members of the project team and key GSK stakeholders. Results or discussions will			

Interim Analysis	Details (Protocol Defined)					
	not be circulated to blinded staff involved in the conduct of the study at the sites.					
Interim 2	 Formal unblinded interim analysis will be conducted during part B. The PASI and PLSS will be evaluated when the last psoriasis patient in cohort 9 has completed D43 visit, and the full interim 2 evaluation will be conducted after all patients have completed their day 85 visit. Data for healthy volunteers and psoriasis patients will be included. 					
	 The purpose of this interim analysis is to provide the project team and GSK stakeholders with key data to inform internal decision making, in order to plan future studies within the clinical development for the asset. 					
	There are no planned implications for the conduct of the study.					
	 Appropriate data summaries will be at the subject and treatment group level for key endpoints of interest and the circulation of results will be restricted to selected members of the project team and key GSK stakeholders. Results or discussions will not be circulated to blinded staff involved in the conduct of the study at the sites. 					

3.2. Final Analyses

Final analyses will be reported when all subjects in all cohorts have completed their final scheduled visits (combined follow-up/surveillance visit or surveillance telephone call), and the following sequential steps have occurred:

- All subjects have completed the study as defined in the protocol.
- All required database cleaning activities have been completed and final database release and database freeze has been declared by Data Management.
- All criteria for unblinding the randomisation codes have been met.
- Randomisation codes have been distributed according to RandAll NG procedures.

4. ANALYSIS POPULATIONS

Population	Definition / Criteria	Analyses Evaluated
Screened	All participants who were screened for eligibility	 Study Population
Safety	 All randomized participants who received at least one dose of study treatment. This population will be based on the treatment the subject actually received. Note: Participants who were not randomized but received at least one dose of study treatment should be listed. 	Study PopulationSafetyEfficacyPDIg
Pharmacokinetic (PK)	 All participants in the Safety population who had at least 1 non-missing PK assessment (Non-quantifiable [NQ] values will be considered as non-missing values). This population will be based on the treatment the subject actually received. 	• PK

Refer to Appendix 9 which details the population used for each display.

4.1. Protocol Deviations

Important protocol deviations (including deviations related to study inclusion/exclusion criteria, conduct of the trial, patient management or patient assessment) will be summarised and listed, separately for healthy volunteers and psoriasis patients.

Protocol deviations will be tracked by the study team throughout the conduct of the study in accordance with the Protocol Deviation Management Plan (30 September 2015 - version 2).

- Data will be reviewed and deviation will be finalised before freezing the database to ensure all important deviations are captured and categorised on the protocol deviations dataset.
- This dataset will be the basis for the summaries and listings of protocol deviations.

A listing of all inclusion/exclusion criteria deviations will also be provided, separately for healthy volunteers and psoriasis patients. This listing will be based on data as recorded on the inclusion/exclusion page of the eCRF.

5. CONSIDERATIONS FOR DATA ANALYSES AND DATA HANDLING CONVENTIONS

- There are no planned examination of covariates and subgroups.
- There are no planned adjustments made for multiple centres in this study.
- There are no planned adjustments for multiple comparisons or multiplicity.

5.1. Study Treatment & Sub-group Display Descriptors

	Treatment Group Descriptions					
	RandAll NG	Output	Output			
Code	Description	Treatment Label	Order			
A	0.0003mg/kg GSK2831781 IV single dose	0.0003mg/kg (ADA-ve)	2			
В	0.0015mg/kg GSK2831781 IV single dose	0.0015mg/kg (ADA-ve)	3			
С	0.0075mg/kg GSK2831781 IV single dose	0.0075mg/kg (ADA-ve)	4			
D	0.04mg/kg GSK2831781 IV single dose	0.04mg/kg (ADA-ve)	5			
Е	0.15mg/kg GSK2831781 IV single	0.15mg/kg (ADA-ve)	6			
	dose	0.15mg/kg (ADA+ve)	7			
		0.15mg/kg Combined	8			
F	0.5mg/kg GSK2831781 IV single dose	0.5mg/kg	10			
G	1.5mg/kg GSK2831781 IV single dose	1.5mg/kg	11			
Н	5mg/kg GSK2831781 IV single dose	5mg/kg	12			
P	Placebo IV single dose	Placebo for HV Combined	1			
		Placebo for PSO	9			

Notes:

- 1. ADA status as defined at screening
- 2. Combined treatment groups include subjects with ADA-ve and ADA+ve (only for healthy volunteers (HV))

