additional 5 active and 5 placebo subjects will be dosed (no more than 2 subjects per day with dosing separated by at least 1 hour). Once data up to 28 days post dose has been collected for all subjects within the cohort, the DEC will review the safety data along with the available PD data, before dosing a cohort of healthy volunteers with pre-existing ADA, at the same dose, without DTH.

A study schematic giving an overview of the visits is in Section 3.1.

Screening - Subjects will attend screening up to 35 days before the first PPD challenge.

Day 1 to Day 3 - Subjects will attend the unit on Day 1 and will receive ID injections of PPD as per Section 5.10.1 and Section 6.5.1. A skin biopsy will be taken from one of the DTH sites as detailed in Section 6.8.1.

Day 28 to Day 32 - After a period of at least 28 days (\pm 3 days) from the first challenge, subjects will return to the unit and will remain resident in the unit from Day 28 (\pm 3 days) until at least 72 hours after dosing. Subjects will receive ID injections of PPD as per Section 5.10.1 and Section 6.5.1. A skin biopsy will be taken from one of the DTH sites as detailed in Section 6.8.1. Provided there are no safety issues and there are no clinically significant haematology results on Day 32 (72 hours post dose) the subject will be discharged from the unit.

Days 36 and beyond dependent on dose group - Subjects will attend the unit as an out-patient.

Follow-up - Subjects will return for a follow-up as specified in Table 1

As the follow-up visit is at approximately 6 months (190 days post-dose, as per Table 1), subjects in the 0.15mg/kg cohort do not require an additional post-dose surveillance visit at 6 months and will only attend a surveillance visit at 12 months.

PART B

Psoriasis patients

At the beginning of Cohort 7, sentinel dosing in subjects without pre-existing ADA will occur such that one subject will receive active and one subject will receive placebo. After review of the two sentinel subjects' safety data (Cohort 7) at 48 hours post-dose, an additional 5 active (3 without and 2 with pre-existing ADA) and 2 placebo subjects (1 with and 1 without pre-existing ADA) will be dosed (no more than 2 subjects per day with dosing separated by at least 1 hour).

All subsequent cohorts do not require stratification for pre-existing ADAs.

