Measuring depletion of LAG-3+ T cells in psoriasis lesional biopsies is anticipated to be more challenging than in a PPD DTH challenge as T cell activation is asynchronous, hence the study in patients will be focused on doses at or above doses that are anticipated to demonstrate pharmacology in healthy volunteers following a DTH challenge.

Test of proof of mechanism in psoriasis patients will be carried out using psoriasis disease endpoints such as lesional plaque biomarkers like epidermal thickness and CD3+ T cell numbers. Clinical response in psoriasis patients will be measured using PASI and PLSS.

Dose escalation in psoriasis patients will be started at one dose higher than the maximum dose investigated in healthy volunteers following a DTH challenge. The overall total number of LAG-3+ cells in the whole body is not anticipated to be markedly different between healthy volunteers with a DTH challenge and patients with mild to moderate psoriasis. However, LAG3+ T cells in skin lesions of psoriasis patients are likely to be higher and that could result in the need for higher doses compared to the dose showing pharmacological activity in healthy volunteers following a DTH challenge. Dose escalation will therefore continue in psoriasis subjects until a significant clinical response is seen (Section 5.4) or the maximum dose is achieved.

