Due to the presence of pre-existing ADA in a variable percentage in sera from both healthy and psoriatic human subjects, the initial investigation of GSK2831781 will be carried out initially in ADA negative subjects in Part A of the study to minimise the potential for diluting/confounding a signal of pharmacological or clinical response. However, for GSK2831781 to have development potential, it will need to be used in a mixed ADA population. Therefore, after initial 28 day safety information is available for the DTH cohort at the highest dose for healthy volunteers, an additional cohort of healthy volunteers (without DTH) with pre-existing ADA will be dosed at the same dose level. Subjects in the psoriasis Cohort 7 will be recruited according to the following stratification: 4 ADA negative on active: 2 ADA negative on placebo and 2 ADA positive on active: 1 ADA positive on placebo. Stratification for pre-existing ADAs in subsequent cohorts is not required. Subject follow-up visits will occur when GSK2831781 plasma concentrations are on average around the EC50 value of the *in vitro* depletion assay in human plasma (See Table 1 and Figure 1). This criteria was selected based on the theoretical possibility that GSK2831781 may still be able to deplete LAG-

3+ T cells and affect the immune system, requiring monitoring of infection risk and applying restrictions for immunosuppressives use and travelling to endemic areas. Thus the period between final dosing and follow up will vary depending on the dose received. The time of the follow-up may be revised based on emerging data collected during the study.

In addition, it is not known whether there will be any long term PD effect, beyond the follow-up time at which levels of GSK2831781 would be negligible, for example by prolonged activity due to slow repletion of LAG-3+ cells. Therefore all subjects in Part A will have a 12 month long term surveillance visit for assessment of safety and tolerability, as well as repeat of immune cell phenotyping and other pharmacodynamic assessments, which are still considered clinically abnormal at the follow-up visit. Subjects on lower doses, where follow-up is less than 6 months, will also have an interim 6 month long term surveillance visit. See Section 6.3.5.2 for repeat PPD challenge for subjects with persistent reduction of the DTH challenge.

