4.2.2. Exclusion Criteria

A subject will not be eligible for inclusion in this study if any of the following criteria apply:

- 1. Received live vaccine(s) (attenuated or recombinant) within 4 weeks of Day 1 or plan to receive a live vaccination during the study until follow-up.
- 2. Subjects who have history of tuberculosis or have close family members with confirmed MTB infection or who are positive at screening by Quantiferon testing.

- 3. Subject is unable to abstain from travelling to areas with high endemic rates of infectious diseases until the end of the follow up period.
- 4. A medical history of severe allergic reaction, angio-edema, anaphylaxis or immunodeficiency.
- 5. Subjects with neutrophil results below the normal range at screening and baseline.
- 6. Subjects with any clinical, even mild, GI upset such as, but not limited to, diarrhea or abdominal cramping during the previous week before dosing, as well as history of more chronic GI upset, e.g. IBS
- 7. Current evidence of ongoing or acute infection within 3 months prior to the first dose of study drug, such as:
 - Serious local infection (e.g. cellulitis, abscess)
 - Systemic infection (e.g. pneumonia, septicaemia, TB)
- 8. **Part A (only cohorts, 1-4 without DTH challenge, and DTH cohort 5) only:** Subjects who test positive for pre-existing ADA to GSK2831781 at screening.
- 9. History of malignancy.
- Current or chronic history of liver disease, or known hepatic or biliary abnormalities (with the exception of Gilbert's syndrome or asymptomatic gallstones). Part A only: Subjects with an aspartate aminotransferase and/or gamma glutamyltransferase level above the upper limit of normal at screening and/or baseline will be excluded.
- 11. History of regular alcohol consumption within 6 months of the study defined as:

an average weekly intake of >21 units for males or >14 units for females. One unit is equivalent to 8g of alcohol: a half-pint (~240 ml) of beer, 1 glass (125 ml) of wine or 1 (25 ml) measure of spirits.

- 12. History of sensitivity to any of the study medications or PPD challenge agent, or components thereof or a history of drug (or IgG therapeutic antibodies) or other allergy that, in the opinion of the investigator or GSK Medical Monitor, contraindicates their participation.
- 13. A positive pre-study Hepatitis B surface antigen or Hepatitis B core antibody, or positive Hepatitis C antibody result within 3 months of screening.

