5.3. Treatment Assignment

Subjects will be assigned to receive GSK2831781 or placebo in accordance with the randomisation schedule generated by Clinical Statistics, prior to the start of the study, using the validated internal software RandAll NG.

The randomisation schedule will be generated to account for the sentinel subjects. Where the first two subjects dosed for any given cohort will be randomised so that 1 subject will receive GSK2831781 and 1 subject will receive matching placebo. In Part B, the sentinel subjects will be required to be ADA negative and subsequent subjects will be stratified by ADA status (ADA negative or ADA positive) as applicable (see Section 3.1.2).

Eligible subjects will receive a unique subject number which will be assigned in chronological order. Once a subject number has been assigned to a subject, it cannot be reassigned to another subject.

Each subject scheduled to receive study drug will also receive a treatment allocation number when randomised. The treatment number will indicate if the subject is to receive the scheduled dose of GSK2831781 or placebo at each dosing occasion.

A description of the projected regimens based on available data is provided in the table below:

Regimen	Description	Ratio (Active:Placebo)
А	0.0003mg/kg GSK2831781 IV single dose	1:1
В	0.0015mg/kg GSK2831781 IV single dose	1:1
С	0.0075mg/kg GSK2831781 IV single dose	3:1
D	0.04mg/kg GSK2831781 IV single dose	3:1
E	0.15mg/kg GSK2831781 IV single dose	1:1 for HV DTH (ADA-) 3:1 for HV No DTH (ADA +)
F	0.5mg/kg GSK2831781 IV single dose	4:2 for psoriasis (ADA-) 2:1 for psoriasis (ADA+)
G	1.5mg/kg GSK2831781 IV single dose	6:3 for psoriasis
Н	5mg/kg GSK2831781 IV single dose	6:3 for psoriasis
Р	Placebo IV single dose	N/A

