6.3.5.2. Follow-up of healthy volunteers who exhibit reduction of PPD challenge

Healthy volunteers will undergo a first PPD DTH ID challenge on Day 1 and then on Day 30 (24 hours post GSK2831781 infusion) as described in Section 3.2. Healthy volunteers who produce an induration of ≥ 6 mm in the post dose challenge, will not require further PPD DTH ID re-challenges. However, subjects who produce a DTH induration of < 6 mm (i.e. exhibit reduction), will have a PPD DTH ID re-challenge after a further 3 months. If they still produce an induration of < 6 mm, it is likely that they will be PPD ID re-challenged every 3 months until the DTH induration is ≥ 6 mm dependent on review by the DEC.

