14.7.2. Pharmacokinetic / Pharmacodynamic Methodology

An exploratory graphical analysis of the data will be performed by generating the plots as presented in Appendix 9.

Model development will be data driven.

The initial PK model of choice will be a compartmental model with linear and nonlinear drug elimination. Further model testing will include, but it is not limited to, a compartmental model with target mediated drug disposition (TMDD) and a minimal PBPK model with TMDD incorporated. We anticipate TMDD to be driven by soluble LAG3 (sLAG3). However, if data allow, we plan to test also more complex models with TMDD driven by both, sLAG3 and T-cell bound LAG3.

The final PK model, possibly incorporating TMDD, will be used to develop a PK-RO model. Data relative to CD4+CD45RA- cell count will be used to model RO (quantified by J11L1 marker) and T-cell depletion (quantified by 1B4 marker). The initial RO model will likely be an Emax model. More complex models might be investigated if the data support it.

If plots (and summary) of NCA derived PK parameters identified ADA status, and/or HV vs Pso as possible significant covariates, we will investigate the influence of these covariates in the PK and RO models. Other covariates may be explored as appropriate.

CONFIDENTIAL

200630

Model acceptability will be judged by convergence, covariance estimation and standard goodness-of-fit plots that may include, but are not limited to:

- Population and individual predictions versus observations
- Conditional weighted residuals versus population predictions and time

For the final PK and the final RO models visual predictive checks (VPCs) will be conducted to assess graphically whether simulations from the developed models are able to reproduce both the central trend and variability in the observed data from the current study as a function of time.

The VPC will be based on 1000 simulations with the model and the design structure of the observed data (i.e. dose level and time, time of PK sampling and individual values of model covariates, if any). The median and the 10th and 90th will be compared to the observed data. Stratification by dose level of GSK2831781 will be used. Other stratification, such as healthy/ psoriasis will be applied in case these covariates were tested in the model.

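### At 0.15 mg/kg in healthy volunteers, ADA status and PPD challenge are one and the same split, yet SAP 5.1 labels the groups by ADA alone and pools challenged with unchallenged placebo subjects

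*SAP*

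**What the plan says.** **Design.** Protocol 4.2.2, criterion 8, bars "Subjects who test positive for pre-existing ADA to GSK2831781 at screening" from cohorts 1 to 5. Protocol 3.3.1 then adds cohort 6: "an additional cohort of healthy volunteers (without DTH) with pre-existing ADA will be dosed at the same dose level". The regimen table in Protocol 5.3 gives the 0.15 mg/kg allocation as "1:1 for HV DTH (ADA-) 3:1 for HV No DTH (ADA"-positive).

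Only cohort 5 receives PPD. Protocol 6.3.5.2 places the challenges as "first PPD DTH ID challenge on Day 1 and then on Day 30 (24 hours post GSK2831781 infusion"). Cohort 5 also requires BCG vaccination (Protocol 4.2.1, criterion 4) and an induration of at least 6 mm to PPD (Protocol 5.10.1).

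**Display groups.** SAP 5.1 labels the 0.15 mg/kg groups ADA-ve, ADA+ve and Combined, and notes: "Combined treatment groups include subjects with ADA-ve and ADA+ve (only for healthy volunteers (HV"). All healthy-volunteer placebo goes into one column. The notes to SAP Table 3.1 (adverse events) name that column, and the eight-group laboratory and vital-sign tables imply it. The induration tables (2.1 to 2.3) and the skin LAG-3+/CD3+ tables (6.1, 6.4) instead use DTH-only groups and identify DTH with ADA-negative.

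**ADA analysis.** The effect of pre-existing ADA on PK is an exploratory objective in both documents. SAP 14.7.2 says that if the non-compartmental PK plots and summaries "identified ADA status, and/or HV vs Pso as possible significant covariates, we will investigate the influence of these covariates".

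**The concern.** A reader of the healthy-volunteer tables will see two groups at the same dose that appear to differ only in ADA status. Any difference between them in late PK, sLAG-3 or activated T cells invites the conclusion that pre-existing antibody caused it. It could equally come from four intradermal PPD injections given the day after dosing, or from selecting cohort 5 for BCG history and PPD reactivity.

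The pooled placebo column raises a second problem. It is neither the right comparator for the unchallenged dose groups nor for cohort 5. Inflammatory cytokines, adverse events and laboratory data are primary safety endpoints, and SAP 7.2 counts G-CSF among the cytokines. Baseline for these blood markers is pre-dose (SAP 5.2), so change from baseline does not remove the effect of a challenge given 24 h after dosing.

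**Working it through.** **1. Reproduce the planned totals.** From Protocol Table 1 and Section 3.2 (for cohort 5, a 1:1 sentinel pair and then "additional 5 active and 5 placebo subjects will be dosed"):

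| Cohort | Dose (mg/kg) | Active | Placebo | PPD | ADA |
|---|---|---|---|---|---|
| 1 | 0.0003 | 1 | 1 | no | - |
| 2 | 0.0015 | 1 | 1 | no | - |
| 3 | 0.0075 | 6 | 2 | no | - |
| 4 | 0.04 | 6 | 2 | no | - |
| 5 | 0.15 | 6 | 6 | yes | - |
| 6 | 0.15 | 6 | 2 | no | + |

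Active: 1+1+6+6+6+6 = 26. Placebo: 1+1+2+2+6+2 = 14. Total 40, as in Protocol 9.2.1.

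**2. Share of challenged subjects by display group.** Pooled placebo 6/14 = 0.43 (8 unchallenged, 2 of them ADA-positive). The 0.15 mg/kg ADA-negative group 6/6 = 1. The ADA-positive group 0/6 = 0. Combined 6/12 = 0.50. Lower doses 0/14 = 0.

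**3. Shift for an additive PPD effect d.** Shift = (challenged share in the group minus challenged share in the comparator) × d.

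- Unchallenged dose groups, including ADA-positive, minus pooled placebo: (0 - 0.43)d = -0.43d
- Cohort 5 minus pooled placebo: (1 - 0.43)d = +0.57d
- 0.15 mg/kg Combined minus pooled placebo: (0.50 - 0.43)d = +0.07d
- ADA-positive minus ADA-negative: (0 - 1)d = -d

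**4. Aliasing.** Among the 12 active subjects at 0.15 mg/kg, a design matrix with intercept, ADA and PPD has rank 2 out of 3. Across all 40 volunteers, with dose groups, ADA and PPD as additive terms, the design has full rank (8 of 8), because the placebo subjects help. Once ADA and PPD may each modify the drug effect, it drops to 9 of 10. PK has no placebo data, so placebo subjects cannot help there.

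**5. Which samples can be affected.** The re-challenge is at 24 h post-infusion. Counting scheduled post-dose samples later than that in Protocol Table 8:

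| Measure | Post-dose samples | After 24 h |
|---|---|---|
| Cytokines | 4 | 1 (48 h) |
| Flow cytometry | 9 | 7 |
| sLAG-3, G-CSF | 10 | 8 |
| Blood transcriptomics | 1 (24 h) | 0 |

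Cmax and the 6 h and 12 h samples precede the re-challenge. The 24 h samples fall at its nominal time, and the draw order is not stated. Before that point the cohorts differ only by the first challenge about four weeks earlier, a biopsy, and the selection criteria.

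**6. Precision after splitting placebo** (SE of a difference in means, in units of the common SD σ). Pooled 6 v 14: √(1/6 + 1/14) = 0.49. No-DTH 6 v 8: √(1/6 + 1/8) = 0.54. DTH 6 v 6: √(1/6 + 1/6) = 0.58. A placebo-corrected ADA contrast has SE √(1/6 + 1/2 + 1/6 + 1/6) = 1.00, against 0.58 uncorrected. It also needs PPD not to modify the drug effect.

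**The case against.** **The displays are descriptive.** There are no formal hypotheses. Cytokines, flow cytometry and sLAG-3 are summarised without a planned active-minus-placebo estimate. Where healthy-volunteer PD is modelled (induration, skin LAG-3+/CD3+), the SAP already uses a DTH-only placebo. This stands: no error rate is at risk, and it would be too broad to say that no dose group ever has a like-for-like placebo.

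**Pooling is partly inferred.** The cytokine, flow and sLAG-3 entries in SAP Appendix 9 do not list their columns, and the mock shells are not in the document. The pooled column there follows only from SAP 5.1. Listings and individual plots would let a careful reader separate the cohorts. This also stands.

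**The covariate list is open.** Directly after the sentence on ADA and population, SAP 14.7.2 leaves room for further covariates. PPD is unnamed, but not excluded.

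**There is other ADA evidence.** Psoriasis cohort 7 examines ADA without PPD, but with only 2 planned ADA-positive active subjects.

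**A stronger reading that fails.** A reader might take the AUC at 0.15 mg/kg (208 observed against 1807 µg·h/mL predicted, an 8.7-fold gap) as a sign that the challenge consumed drug. Protocol Table 2 does not support that. The gap is larger in unchallenged cohorts: 90.3/1.38 = 65-fold at 0.0075 mg/kg and 482/25.4 = 19-fold at 0.04 mg/kg. It is 6023/903 = 6.7-fold in unchallenged psoriasis patients at 0.5 mg/kg. It shrinks with dose regardless of PPD, and the 208 is not attributed to cohort 5 or cohort 6. Protocol 3.3.1 does say that the whole-body LAG-3+ cell load is "not anticipated to be markedly different between healthy volunteers with a DTH challenge and patients with mild to moderate psoriasis". That makes a PPD effect on disposition conceivable; it does not say that the challenge changes clearance. SAP 14.7.2 expects target-mediated disposition to be driven by soluble LAG-3, and neither document says that PPD alters it.

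**Conclusion.** The labelling and pooling in SAP 5.1 should be changed. At 0.15 mg/kg, ADA status and PPD challenge cannot be told apart from that contrast, and the pooled placebo column is 43% challenged. The shifts are -0.43d, +0.57d and, for the ADA contrast, -d. They assume an additive PPD effect and the planned cohort sizes; d is unknown and could be negligible for some markers.

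For the acute re-challenge, the scope is the 48 h cytokine sample; G-CSF, flow cytometry and sLAG-3 from 72 h; later adverse events and laboratory values; and late PK. A reader might infer that all healthy-volunteer cytokine and PD data are confounded with it. The sampling times do not support that for Cmax or for the 6 h and 12 h samples.

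Two SAP entries make the missing label more than cosmetic. Note 2 in SAP 2.3 says that the DTH cohort has pre-existing ADA, and Table 3.5 draws ADA-positive healthy volunteers from cohort 5. Both contradict Protocol Table 1 and the SAP's own identification of DTH with ADA-negative.

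**What to change.** 1. In SAP 5.1, split healthy-volunteer placebo into Placebo, no DTH (cohorts 1-4 and 6, n = 8) and Placebo, DTH (cohort 5, n = 6). The combined column may be kept as an extra.
2. Relabel the 0.15 mg/kg groups ADA-ve, DTH and ADA+ve, no DTH.
3. Read each group against its matching placebo for adverse events, laboratory data, cytokines, G-CSF, flow cytometry and sLAG-3, and state the columns in Appendix 9.
4. State that the 0.15 mg/kg contrast alone does not estimate the ADA effect on PK or PD. Splitting placebo does not cure this aliasing, and PK has no placebo.
5. In SAP 14.7.2, name PPD challenge as a covariate to examine whenever ADA is tested. Say that separating the two depends on the model: it comes through the dose structure, across clearly non-linear PK, and through cohort 7 with its 2 planned ADA-positive actives.
6. Reconcile SAP 2.3 note 2 and Table 3.5 with Protocol Table 1.

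Cost: label changes, one extra column and one named covariate. The placebo columns shrink from 14 to 8 and 6, so the SE of a difference rises from 0.49σ to 0.54σ or 0.58σ. No new data are needed.
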